Identifiers: NCT04814342 Protocol ID: 70Ag_Vital-00008

Title: Accuracy of Pulse Oximeters With Profound Hypoxia During Motion (NIHO12)

Original Date: 16 Mar 2021

Redaction: 1 Sep 2025

Determination of SpO₂ and PR accuracy specifications during motion
ACCURACY OF PULSE OXIMETERS WITH PROFOUND HYPOXIA NIHO12
Pulse Oximeter Accuracy Evaluation Protocol
During Controlled Motion

Study Site: The UCSF Hypoxia Research Laboratory, [name]

Principal Investigator (PI): [name]

Study Period: March 25, 2021

Breathe-down Test During Motion

1. Objective

This study is intended to evaluate performance of the following pulse oximeter:

Device name	Model name	Quantity	Intended populations	Materials that will be in contact with subject's skin
Pulse oximeter	OVL-4000 series, OLV-4202 (SW version: 01-11)	4	Adult/Child/Neonate	-
Disposable probe	TL-273TA	5	Adult/Neonate	Polyurethane, polyester, acrylic adhesive
Disposable probe	TL-535U	1	Neonate/Preterm infant	-
Attachment tape	XL (option for TL-535U)	5	Neonate	Polyurethane, Styrene-based elastomer
Multi-site probe	TL-220T	1	Adult/Child/Neonate	-
Attachment tape	- (option for TL-220T)	5	Adult/Child/Neonate	Polyvinyl chloride
Multi-site Y probe	TL-260T	1	Adult/Child/Neonate/ Preterm infant	-
TL-260T clip adapter	- (option for TL-260T)	1	Adult	Silicone

SpO₂ probe, TL-281-IB will be used for monitoring SpO₂ for reference. Bedside monitor, PVM-4763 (SW version 01-10) will be used for monitoring heart rate for reference. All test devices can be identified by serial number or lot number. Nihon Kohden will be responsible of keeping records documenting the delivery, use, return, and disposal of the test devices.

The following requirements are to be met during motion:

- SpO₂ value range 70% to 100%
- 5 subjects, with 2 of dark pigment

Safety of the test devices will be evaluated by assessing adverse events occurred to subjects.

This test is designed in response to the 2013 FDA Guidance on Pulse Oximeters – Premarket Notification Submissions and by ISO 80601-2-61:2017 on Pulse Oximeters, specifically the sections listed below.

- 2013 FDA Guidance on Pulse Oximeters – Premarket Notification Submissions:
 - o 4.1 Accuracy of Pulse Oximeters
 - o 4.1.1 In vivo testing for SpO₂ accuracy under laboratory conditions
 - o 4.1.3 Testing for SpO₂ accuracy for oximeters making motion performance claims
 - o 4.1.5 Testing for Pulse Rate Accuracy claims
 - o 4.1.6 Testing for Pulse Rate Accuracy for oximeters labeled with motion performance claims
- ISO 80601-2-61:2017 Annex EE.2 and clause 201.12.1.101.2
 - o 201.12.1.101 SpO₂ accuracy of pulse oximeter equipment

- o 201.12.1.101.2 Determination of SpO₂ accuracy
- o 201.12.1.102 Accuracy under conditions of motion
- o 201.12.1.104 Pulse rate ACCURACY

NOTE: This study has been designed per ISO 80601-2-61:2017, and it has been also designed to respond to the recommendations on subject safety added on ISO 80601-2-61:2011. Since ISO 80601-2-61:2011 has been updated as ISO 80601-2-61:2017 with no changes in the requirements for conducting the study and demonstrating SpO₂ and PR accuracy, this study results can be referred for demonstrating SpO₂ and PR accuracy per ISO 80601-2-61:2011 as well as per ISO 80601-2-61:2017.

This study will be conducted in accordance with the ethical principles that have their origin in the Declaration of Helsinki, ISO 14155:2011 and :2020.

2. Subjects

This study is performed on volunteers who have previously been determined to be healthy enough for this study, have signed an informed consent form and met the following IRB requirements. These volunteers are compensated by the laboratory for their participation. Point of enrolment is defined as time at which subjects sign and date the informed consent form and screening based on subject demography and inclusion/exclusion criteria is complete. Expected duration of each subject's participation will be about 45 minutes.

The inclusion criteria for the test subjects are:

1. Both male and female subjects who can give written informed consent
2. Healthy subjects capable of undergoing controlled hypoxemia to the levels outlined in the desaturation profile below
3. Meeting the demographic requirements listed above.

The exclusion criteria for the test subjects are:

1. Age below 18 or over 50
2. Pregnant women
3. Significant arrhythmia
4. Blood pressure above 150 systolic or 90 diastolic
5. Subjects whom the investigator consider ineligible for the study.

5 subjects will be recruited to complete the test. Of these 2 will be dark pigment.

3. Desaturation

Each subject shall have their right arm positioned on a motion generating machine. The right hand is called the motion hand, the left is called the control hand.

For each subject, a series of desaturation runs are performed. Run 1 starts with a stabilized period at room air and is followed by stabilized plateaus at various lower saturation levels. Run 2 starts with a stabilized period at 100% and is followed by stabilized plateaus at various lower saturation levels. The following are value targets:

Run 1	room air, 90%, 80%, 70%
Run 2	100%, 95%, 85%, 75%

The objective of these targets is to spread the data points evenly over the desired range. Achieving them exactly is not important, though every effort will be made to be within 2%.

The SpO₂ value is reduced by delivering a mixture of medical air and nitrogen, controlled by 2 manually controlled needle valve flowmeters. The operator controls the SpO₂ by observing the breath by breath arterial saturation, which is in turn computed from end tidal PO₂ and PCO₂. FiO₂ is reduced suddenly at first then adjusted to achieve a stable plateau value at the desired target. A plateau is defined as stable when the readings of the sponsor Control instruments have not changed more than 1 % for 20 seconds (they do not have to agree with each other). Each desaturation plateaus should not exceed 10 minutes. When the

sponsor confirms that stability is achieved, the plateau is held for 90 seconds. The gas mixture is then changed for the next value. This is then repeated for each plateau value.

During this procedure, the subject is coached on breathing. If he/she appears to fall asleep, he/she is woken up. At any signs of distress, he/she is given 100% oxygen.

Each run should take Between 15 and 25 minutes. It is normal to schedule as many as 10 subjects per day.

Trained Nihon Kohden personnel will be present at the procedure. The role of the Nihon Kohden person is to give technical support relative to the use of the test pulse oximeters and to perform study monitoring. All these actions will be done under the careful direction of the investigator.

Data of the test devices will be obtained in an SD card inserted into the pulse oximeter OLV-4202. Subject's demographic data will be collected using specific data collection forms.

4. Reference Data

The reference SpO2 will be measured using a Nihon Kohden OLV-4202 as a secondary standard pulse oximeter equipment. The equipment should be quality control checked at the study site to be functioning properly before use.

The heart rate will be measured using a Nihon Kohden PVM-4763 as an ECG monitor. The monitor should be quality control checked at the study site to be functioning properly before use.

5. Motions

This study evaluates the effect of several motions. The main attributes are rubbing and tapping. For each subject one run will use tapping and the other rubbing. Motion types will be arranged as follows:

On the motion-hand side

	Subject 1 + 3 + 5	Subject 2 + 4
Run 1	rubbing	tapping
Run 2	tapping	rubbing

Each of these motions can be driven in the following ways.

- 2Hz sine (2Hz)
- 4Hz sine (4Hz)
- Sequence of moves of a pseudo random distance from 1mm to 30mm (Rand)
- The amplitude of the sine motion and the maximum slope of the random motion will be determined at the beginning of each Desaturation Run.
- For 2Hz sine and 4Hz sine, motion artifact red p-p amplitude will be equal to the PPG p-p amplitude of the subject. For Rand, the largest motion artifact red p-p amplitude will be equal to the PPG p-p amplitude of the subject.

In each plateau, the motion drive type will be sequentially changed in the following ways.

- 30 seconds' no motion
- 30 seconds' 2Hz
- 30 seconds' 4Hz
- 30 seconds' Rand

6. Sensor Placements

A reference SpO2 will be taken on each subject with the sponsor Control instrument. The SpO2 probes for the sponsor Control instrument will be the TL-281-IB disposable SpO2 probes. These probes will be arranged as follows:

On the control-hand side

	Subject 1 + 4	Subject 2 + 5	Subject 3

TL-281T-IB	Middle	Ring	Index
------------	--------	------	-------

A 3-lead ECG will be taken on each subject with the sponsor Control instrument. The electrodes for the sponsor Control instrument will be the L-150X disposable ECG electrodes.

The probes for the primary test instruments will be the TL-273TA Neonatal and Adult disposable probe, the TL-535U Neonatal disposable probe, the TL-220T Multisite reusable probe. These probes will be arranged as follows:

On the motion-hand side

	Subject 1 + 4	Subject 2 + 5	Subject 3
TL-273TA	Index	Middle	Ring
TL-535U	Middle	Ring	Index
TL-220T	Ring	Index	Middle

7. Subject Safety

The sensors will be isolated as follows

1. 500V between the sensor and earth ground
2. 4 KV between AC mains power and the low voltage power supply and 1.5 KV between the low voltage power supply and the sensor, OR 5 KV between AC mains and the sensor.

Non-invasive blood pressure will be measured at a screening. EtCO₂, respiratory rate, and FiO₂ of the subjects will be monitored. In addition, the laboratory maintains criteria for subject selection that have been proven to minimize the risk of any problems during the study.

Adverse event and serious adverse event will be assessed throughout the study by the Principal Investigator and Co-Investigator or research nurse designated by Principal Investigator. If any adverse event occurs during the study, an appropriate medical treatment will be provided to the subject by a medical staff at the laboratory. Nihon Kohden may suspend or prematurely terminate the study when there are serious violations and deviations from the GCP which could adversely affect subject's safety and correct data recording.

The test will be discontinued when a subject requests to withdraw from the study or the Co-investigator will terminate the desaturation procedure and/or a subject's participation in the study because of the reasons including: 1) the subject experiences unexpected oxygen desaturation or 2) the subject loses consciousness.

Risks associated with participation in the study include the following:

- a. The risks of the brief exposures to hypoxia are include feeling short of breath, headache, and dizziness. Brief loss of consciousness may occur but is not expected at the levels of oxygen targeted for these tests.

Nihon Kohden has determined that there is no residual risk associated with the test devices. Nihon Kohden will be responsible for maintaining the test devices.

8. Data Analysis

Data from subjects who did not complete the protocol will be thrown out. Missing data will not be supplemented.

Data points at a plateau where the equipment output for TL-281-IB changes over 2% saturation will be thrown out.

Data from unstable pulse wave signal due to the uncontrolled motion will be thrown out.

SpO₂ data will be reduced using the ARMS method and accuracy will be reported as the ARMS deviation between the co-oximeter and the test instruments for all points gathered from each sensor.

$$A_{rms} = \sqrt{\frac{\sum_{i=1}^n (SpO_{2i} - S_{Ri})^2}{n}}$$

PR data points where heart rate changes over 4bpm for 10 seconds will be thrown out.

PR data points at a plateau where heart rate changes over 19bpm for 10 seconds will be thrown out.

PR data will be reduced using the ARMS method and accuracy will be reported as the ARMS deviation between the ECG monitor and the test instruments for all plateaus gathered from each sensor. Accuracy will be determined by comparing the noninvasive pulse rate measurement of the pulse oximeter (PRi) to the heart rate obtained from an electrocardiography reference device (HRRi) and calculating the arithmetic root mean square (Arms) error value as follows:

$$A_{rms} = \sqrt{\frac{\sum_{i=1}^n (PR_i - HRR_i)^2}{n}}$$

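### SpO2: Section 8 gives no estimate of the effect of motion, and does not keep no-motion data out of the Arms meant to describe accuracy during motion

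*Combined protocol and SAP*

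**What the plan says.** Section 3 sets the layout: "Each subject shall have their right arm positioned on a motion generating machine", and "The right hand is called the motion hand, the left is called the control hand". Section 6 places TL-273TA, TL-535U and TL-220T on the motion hand and the reference probe, TL-281-IB, on the control hand. The fingers rotate over index, middle and ring across subjects.

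Section 5 opens with "This study evaluates the effect of several motions". It names two motion types, rubbing and tapping, and three drives (2 Hz, 4 Hz and random). The sequence it lists for each plateau begins with "30 seconds' no motion" and then gives each drive 30 seconds. Section 3 says of the same plateau that once the "sponsor confirms that stability is achieved, the plateau is held for 90 seconds".

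Section 8 summarises SpO2 by one Arms per sensor, taken "for all points gathered from each sensor". Its exclusion rules cover subjects who do not complete, plateaus where the reference drifts, and unstable pulse waves from uncontrolled motion. None of them deals with the no-motion block, and no step compares that block with the motion blocks. The document title gives the purpose as accuracy specifications under motion.

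**The concern.** The design lists a baseline with the same subject, finger and probe in every plateau, and Section 5 states an aim that needs it. The analysis section never uses it. The Section 5 aim is therefore left without an estimate for SpO2.

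The second gap affects the headline figure. Read literally, the Section 8 wording takes in the still-hand points. If they are pooled, data recorded without motion enter a number that will be read as accuracy during motion. That number then looks better than the motion blocks alone would show. Two analysts following the text could report different values, because the text does not settle whether still data count.

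**Working it through.** The plan gives no expected Arms, variance, power or acceptance limit, so there is no figure of its own to reproduce.

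**Inputs from the documents**
- Blocks per plateau (Section 5): 4 × 30 s = 120 s, of which 30 s are still. Share of still data w = 30/120 = 1/4, if points are taken evenly in time.
- Stable hold (Section 3): 90 s, which is 30 s short of the listed blocks.
- Plateaus (Section 3): 2 runs × 4 targets = 8 per subject. With 5 subjects that makes 40 still blocks and 3 × 40 = 120 motion blocks per sensor, if all are completed.

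**Inputs assumed**, in SpO2 points, because the documents give none: steady offset b, ordinary still-hand noise s, and added motion error m with no mean shift.

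**1. Dilution by pooling**

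Motion blocks only: Arms² = b² + s² + m². All points: Arms² = b² + s² + (1 − w)m².

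With s = 0, m = 2.0 and w = 1/4:

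| b | Motion blocks only | All points |
|---|---|---|
| 0 | 2.00 | √3.00 = 1.73 |
| 0.5 | 2.06 | √3.25 = 1.80 |
| 1.0 | 2.24 | √4.00 = 2.00 |
| 1.5 | 2.50 | √5.25 = 2.29 |

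- Other values of m, with b = s = 0: m = 1 falls from 1.00 to 0.87, and m = 3 from 3.00 to 2.60.
- With s = 1.0 and b = 0: m = 1.5 falls from 1.80 to 1.64, and m = 2.0 from 2.24 to 2.00.
- The timing conflict changes w. If only 90 s are kept and the still block is among them, w = 1/3 and 2.00 becomes √(4 × 2/3) = 1.63. If the still block lies outside the data used, w = 0 and 2.00 stands.

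**2. Arms cannot stand in for the effect of motion**

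Take all points with s = 0. A sensor with b = 2 and m = 0 has Arms √4 = 2.00. A sensor with b = 1 and m = 2 has √(1 + 3) = 2.00. The first is unaffected by motion and the second is not, yet the reported figure is the same. In motion blocks alone, with m = 2.0, the offset's share b²/(b² + m²) is 6% at b = 0.5 and 36% at b = 1.5. For m = 1 the range is 20% to 69%, and for m = 3 it is 3% to 20%.

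**3. What the still block can recover**

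With s = 1.0 and m = 1.5:

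| b | Arms, still | Arms, motion | √(motion² − still²) |
|---|---|---|---|
| 0 | 1.00 | 1.80 | 1.50 |
| 0.5 | 1.12 | 1.87 | 1.50 |
| 1.0 | 1.41 | 2.06 | 1.50 |
| 1.5 | 1.80 | 2.35 | 1.50 |
| 2.0 | 2.24 | 2.69 | 1.50 |

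The difference of squares is free of the offset as long as motion does not move the mean. If motion shifts the mean by d, it also contains (b + d)² − b² = d² + 2bd, so the mean change has to be reported beside it.

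**4. Hand and finger**

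Swapping hands would not change Arms for an offset that only changes sign. With s = 1.0 and m = 1.5, √(1 + 1 + 2.25) = 2.06 whether the offset is +1 throughout or +1 in half and −1 in half. In the Section 6 tables TL-535U has the same finger position as the reference in 5 of 5 subjects, and TL-273TA and TL-220T in 0 of 5.

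**The case against.** The strongest reply is that the title asks for accuracy during motion and Section 8 labels its Arms as accuracy. For that purpose total error against the reference is the right quantity, and a probe's own offset is part of its accuracy. That one total can arise in several ways is a property of the measure. The Section 5 sentence introduces the description of the drives and is not a formal endpoint. This stands, and it is why the total Arms should be kept. It does not answer the pooling question, because an accuracy figure for motion should not depend on an unstated choice about still data.

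A reader might infer something stronger: that because the test probes are always on the right hand and the reference on the left, fixed hand, finger and probe offsets are being counted as motion error. The documents do not support that:
- Arms is never called motion error.
- Fingers rotate across subjects. What is tied to the probe is whether its finger matches the reference finger.
- Pulse rate is compared with the ECG, so the left-hand probe plays no part there.
- The fixed side is not the operative defect, as the swap calculation shows. It can also be confirmed only for the three placed probes, because TL-260T is listed in Section 1 but has no placement in Section 6.

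It is also fair to say that the within-plateau comparison is imperfect. The still block always comes first and the drives follow in a fixed order, so a change mixes motion with time. The RMS of the changes would not be zero without a motion effect: if two block means carry independent errors of SD e, their difference has RMS e√2. These limits stand and should be stated with the result.

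**Conclusion.** The point holds for SpO2, as a gap in the analysis and not as a fault in the layout. Section 8 has no estimate of the effect of motion, although Section 5 states that aim and lists a baseline for it. As written it also allows still-hand data into the figure for accuracy during motion.

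The dilution is about 13% when the still hand carries no error and a quarter of the data are still (1 − √0.75 = 0.13). It is less in proportion when offset or ordinary noise is present: at m = 2.0 and b = 1.5, with no noise, 2.50 falls to 2.29. These sizes rest on assumed errors and on points spread evenly in time. With no acceptance limit in the documents, it cannot be shown that any pass or fail would change. The correction should be made, but it does not invalidate the total Arms.

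**What to change.** First reconcile the 90-second hold in Section 3 with the 120 seconds of blocks in Section 5, so that it is clear whether the still block lies inside the stable hold. Section 8 also names a co-oximeter as the SpO2 reference where Section 4 names the OLV-4202; these need to agree.

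Then, in Section 8, for SpO2 and each sensor:
1. Calculate the accuracy-during-motion Arms against the reference from the motion blocks only.
2. Report mean bias and Arms separately for the still block and for each drive, by rubbing or tapping. Each type covers 4 plateaus × 5 subjects = 20 plateaus, so each drive-by-type cell has at most 20 blocks from five subjects and should be treated as descriptive.
3. Give the within-plateau change as the estimate of the effect of motion: the motion-block mean difference minus the still-block mean difference, together with Arms² in motion minus Arms² at rest.
4. State that this change is confounded with the fixed block order, and that the RMS of the changes includes ordinary noise.

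The analysis needs no new subjects or equipment and uses blocks that Section 5 already lists, subject to the timing point above. The cost is one more table and possibly a less favourable motion Arms.

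### With no settling rule between the no-motion block and the 2Hz block, still-period values may enter the motion score and can lower the motion Arms

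*Combined protocol and SAP*

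**What the plan says.** Section 5 (Motions) gives one fixed order for every plateau: "In each plateau, the motion drive type will be sequentially changed in the following ways". The list reads "30 seconds' no motion", "30 seconds' 2Hz", "30 seconds' 4Hz", "30 seconds' Rand". No pause or settling time is given between blocks.

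Section 3 (Desaturation) treats a plateau as stable when the "readings of the sponsor Control instruments have not changed more than 1 % for 20 seconds". The plateau is then held for 90 s, and only afterwards is the gas mixture changed.

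Section 8 (Data Analysis) reports the SpO₂ Arms "for all points gathered from each sensor". Its exclusions cover subjects who do not complete, plateaus where the reference moves by more than 2%, pulse-rate points where the heart rate moves too much, and unstable signal from uncontrolled motion. None of them removes readings taken just after motion begins. The plan gives no averaging time for the OLV-4202, no hold behaviour, no scored window within a block, and no statement on whether the no-motion block is scored.

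**The concern.** The stated aim is accuracy during motion. In every plateau the motion hand is first still for 30 s at a saturation that is meant to stay constant, and the 2Hz drive then starts at once. If the test oximeter shows an average over past seconds, its first readings under motion mix still-period signal with motion signal. If it freezes its last good value when the signal is poor, it shows the still-period value outright. Because the saturation is not meant to move, such a reading scores as nearly correct although it was not measured under motion.

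The plan cannot then tell a value tracked through motion from one remembered from the still period. At stake is a motion Arms that may look better than the device's settled performance, by an amount that a reader of the plan cannot bound.

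**Working it through.** The plan states no Arms limit and no figure for this effect, so there is nothing of its own to reproduce.

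**Inputs from the documents**
- Sequence: 4 × 30 = 120 s, of which 3 × 30 = 90 s is motion (Section 5).
- Hold: 90 s (Section 3).
- Plateaus: 5 subjects × 8 targets = 40 (Sections 2 and 3). All 40 planned 2Hz blocks directly follow a no-motion block.

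**Assumptions, not in the documents**
- Error is zero in the still period and constant at e under motion.
- The device uses a moving average of T seconds, or else holds its last still value for H seconds.

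**Averaging.** At t seconds after motion starts, the displayed error is e·t/T for t < T, and e afterwards. Over a scored span of L ≥ T seconds the mean square is e²[(T/3) + (L − T)]/L. The ratio of reported to settled Arms is therefore √(1 − 2T/(3L)). This is √(1 − T/45) for the 2Hz block (L = 30) and √(1 − T/135) for all motion (L = 90).

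| T | Share of 2Hz block | Arms ratio, 2Hz | Share of all motion | Arms ratio, all motion |
|---|---|---|---|---|
| 4 s | 4/30 = 13% | 0.955 | 4/90 = 4% | 0.985 |
| 8 s | 8/30 = 27% | 0.907 | 8/90 = 9% | 0.970 |
| 16 s | 16/30 = 53% | 0.803 | 16/90 = 18% | 0.939 |

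If the motion error is independent zero-mean noise from second to second instead of constant, simulation gives a smaller effect: 0.940 and 0.980 at T = 8 s, and 0.865 and 0.957 at T = 16 s.

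**Hold.** The ratio is √(1 − H/L).
- H = 10 s: √(20/30) = 0.816 in the 2Hz block and √(80/90) = 0.943 over all motion.
- H = 30 s: 0 in the 2Hz block and √(60/90) = 0.816 over all motion, which is 18% too low.

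**Later blocks.** For an averaging window of up to 30 s, nothing from the still period reaches the 4Hz or random block. Those blocks inherit the motion block before them, which can move their error either way. For example, a 2Hz error of size 1 leaking into an otherwise error-free 4Hz block gives that block an Arms of √(T/90), which is 0.21 at T = 4 s and 0.42 at T = 16 s.

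**Timing.** The 120 s sequence is 30 s longer than the 90 s hold. If the no-motion block overlaps the stability period, the three motion blocks fit within the hold. If the sequence starts when stability is confirmed, the random block falls after the gas change, and a stale value need not score as correct there. The documents do not say which applies.

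**The case against.** The strongest reply is that the documents establish a gap in specification and not a bias. That stands. A reader might infer that still-period values do carry over and that the motion Arms is too low. The documents do not support this, because they give neither an averaging time nor a hold behaviour, and with neither feature the ratio is 1. A reader might also infer that Section 8 scores from the first second of each block. Its wording covers all points, but it sets no sampling instant or window, so this is a natural reading and not a stated rule.

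A second reply is that averaging and holding are part of the device as used. This is fair as a choice of what to measure. It does not settle the matter, because each drive lasts only 30 s and the transition can fill a large share of that time, which continuous motion in use need not do. Reporting Arms both ways serves both views.

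A third reply is that the pooled effect of averaging is small. This also stands: 1.5% to 6% for windows of 4 to 16 s. With no Arms limit in the plan, no changed conclusion can be shown. Scoring the no-motion block with zero error would matter more, since √(90/120) = 0.866, but that is dilution and a separate issue.

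Dropping the no-motion block from the score would not answer the point, because the first motion readings would still follow a still period.

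**Conclusion.** The point holds in conditional form. Every planned 2Hz block follows 30 s without motion at a saturation meant to be constant, and no settling rule protects the motion score. If the device averages or holds, early motion readings may contain still-period values and can lower the motion Arms.

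With zero still-period error and constant motion error, averaging over 4 to 16 s lowers Arms by about 5% to 20% in the 2Hz block and 1.5% to 6% over all motion. A 30 s hold would remove all error from the 2Hz block and leave the overall Arms 18% too low. The downward direction assumes that still readings are more accurate than motion readings.

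A reader might conclude that every motion block is flattered by the still period. For averaging windows of up to 30 s that is not so: the 4Hz and random blocks inherit earlier motion, with an effect in either direction. The premise of constant saturation through all three motion blocks also depends on reconciling Sections 3 and 5. This is a cheap improvement, not a demonstrated bias.

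**What to change.** - **Section 5:** set and record one averaging mode for all OLV-4202 test units, with a window T well under 30 s, and state the device's hold behaviour. Record when motion and each drive start on a clock that can be matched to the SD-card data. The documents do not mention such matching.
- **Section 8:** for the pooled motion Arms, exclude the first T seconds after motion starts, that is, the start of the 2Hz block only. For any Arms reported by drive type, exclude the first T seconds of each block. Report Arms with and without this rule.
- **Held readings:** where the device log identifies them, count and report them separately. The documents do not say that it does. The filter alone does not deal with a hold longer than T: with H = 30 s and T = 8 s, 60 of the 82 scored seconds carry the error, so the ratio is √(60/82) = 0.855.
- **Sections 3 and 5:** reconcile the 120 s sequence with the 90 s hold.

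Under the averaging model, the filter restores the ratio to 1. At T = 4, 8 and 16 s the pooled score keeps 86, 82 and 74 of 90 s, and a score by drive type keeps 26, 22 and 14 of 30 s. Dropping T seconds from every block of the pooled score would cost more (3 × 16 = 48 of 90 s at T = 16 s) without removing any further still-period content from averaging.

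The cost is a device setting fixed before data collection, a record of start times, and a time filter in the analysis. If data are already collected, the setting used can be reported, and the filter can be applied if start times are known. The downside is fewer scored seconds and a slightly less favourable Arms.

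### As written, the SpO2 Arms rule in Section 8 lets the 30 s no-motion segment of each plateau into the figure for accuracy during motion.

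*Combined protocol and SAP*

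**What the plan says.** All references are to the combined protocol and SAP.

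- **Purpose.** The title speaks of "accuracy specifications during motion". Section 1 introduces the saturation range and the subject numbers with "The following requirements are to be met during motion". Section 5 opens with "This study evaluates the effect of several motions".
- **Sequence within a plateau (Section 5).** Four states follow one another in each plateau. The first is "30 seconds' no motion"; then come 30 s each of 2Hz, 4Hz and Rand.
- **Plateau timing (Section 3).** A plateau counts as stable when the control readings "have not changed more than 1 % for 20 seconds". After stability is confirmed, "the plateau is held for 90 seconds".
- **Analysis (Section 8).** The SpO2 Arms is taken "for all points gathered from each sensor". Three exclusions bear on SpO2: subjects who did not complete, plateau points where the reference probe output changes by more than 2% saturation, and the rule "Data from unstable pulse wave signal due to the uncontrolled motion will be thrown out". The pulse-rate (PR) Arms is taken over all plateaus from each sensor, with its own heart-rate exclusions.

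**The concern.** A figure offered as accuracy during motion should be calculated from data recorded during motion. Section 5 schedules a still period inside the plateau. Section 8 neither removes it nor limits the calculation to the driven segments; its only exclusion that mentions motion concerns uncontrolled motion.

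Arms is a root mean square over points, so pooling still-hand and motion points gives a weighted mixture of the two squared errors. If the device reads more accurately on a still hand, which is plausible but not stated in the documents, the reported value is more favourable than the motion accuracy it is meant to describe.

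The weight of the still data is not fixed either, because the 120 s sequence does not match the 90 s hold and Section 8 defines no analysis window. The make-up of the main accuracy statistic could therefore be settled after the data are seen.

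**Working it through.** The plan gives no Arms value, acceptance limit or sample-size calculation, so there is no figure of its own to reproduce. The check has three steps.

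**1. Does any rule remove the still segment?** The rule on non-completers removes whole subjects. The 2% rule concerns stability of the reference. The uncontrolled-motion rule concerns unplanned movement. None applies to a planned still period.

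**2. What share f of the analysed time is still?** Inputs: 5 subjects (Section 2), 4 target levels in each of 2 runs (Section 3), and four 30 s segments (Section 5). That makes 5 × 8 = 40 plateaus per sensor. Three readings are possible:

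| Reading | Time per sensor | Still time | f |
|---|---|---|---|
| (a) full sequence analysed | 40 × 120 = 4,800 s | 40 × 30 = 1,200 s | 1/4 |
| (b) only the 90 s hold, filled by the three motion segments | 40 × 90 = 3,600 s | 0 s | 0 |
| (c) the 90 s starts with the still segment and Rand is lost | 40 × 90 = 3,600 s | 1,200 s | 1/3 |

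Reading (b) fits the numbers: 3 × 30 = 90 s, and the 20 s stability check fits inside the 30 s still segment. It is not stated anywhere. Reading (c) has the least textual support. If the two starting levels are left out, f does not change; under (a), 5 × 6 × 30 = 900 s of 5 × 6 × 120 = 3,600 s are still.

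**3. How large is the dilution?** Let r = still-hand Arms / motion Arms. The documents do not give r, so a range is shown. Points are assumed to be logged at an equal rate in every segment. Then

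reported Arms / motion Arms = √(f·r² + 1 − f).

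For example, at f = 1/4 and r = 0.8: √(0.25 × 0.64 + 0.75) = √0.91 = 0.954, an understatement of 4.6%.

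| r (assumed) | f = 1/4 | f = 1/3 | f = 0 |
|---|---|---|---|
| 0 (bound) | 0.866 (−13.4%) | 0.816 (−18.4%) | 1.000 |
| 0.5 | 0.901 (−9.9%) | 0.866 (−13.4%) | 1.000 |
| 0.8 | 0.954 (−4.6%) | 0.938 (−6.2%) | 1.000 |
| 1 | 1.000 | 1.000 | 1.000 |
| 1.2 | 1.054 (+5.4%) | 1.071 (+7.1%) | 1.000 |

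Put the other way, at f = 1/4 the true motion Arms is 1.048, 1.109 or 1.155 times the reported value at r = 0.8, 0.5 or 0.

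The r at which the understatement reaches 5% is √((0.95² − (1 − f))/f):

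- f = 1/4: √((0.9025 − 0.75)/0.25) = 0.781
- f = 1/3: √((0.9025 − 0.6667)/0.3333) = 0.841

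For PR, the rule over all plateaus does not exclude the still segment either. The documents do not say how a plateau contributes values, so no size can be calculated.

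**The case against.** The strongest reply is that a motion-only analysis is plainly intended. The title and objective point to motion, Section 5 lists only 2Hz, 4Hz and Rand as ways of driving the motion, and reading (b) is the only one of the three that fits both stated durations without extending the data window. The Section 8 phrase may mean no more than pooling over subjects and plateaus. The same sentence names a co-oximeter although Section 4 makes a pulse oximeter the reference, so its wording is loose in any case.

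This makes (b) a fair guess at intent, but it does not make it the rule. Reading (b) needs two unstated steps: that the still segment precedes the hold, and that only hold data are analysed. Section 5 places the still segment within the plateau, and Section 8 does not limit the data to the hold. The Section 1 wording about motion governs the saturation range and subject numbers, not the analysis set.

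A second reply is that the percentages are less firm than they look. Section 3 allows a plateau of up to 10 minutes, so a fully literal reading could admit points outside the 120 s sequence. The uncontrolled-motion exclusion could also remove points unequally across segments. Both are correct: f need not be exactly 0, 1/4 or 1/3, and each ceiling holds only for its own f. This adds to the uncertainty about what would be reported and does not remove the problem.

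A third reply is that no consequence is shown. That stands, since there is no acceptance limit to test against.

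**Conclusion.** The concern holds. Followed as written, Section 8 mixes still-hand points into the SpO2 Arms that is meant to describe accuracy during motion.

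With the full sequence analysed (f = 1/4), the understatement is 4.6% at r = 0.8 and 9.9% at r = 0.5. The 13.4% ceiling would need zero still-hand error, and an understatement of 5% or more needs r of about 0.78 or less. There is no bias at r = 1 or under reading (b), and the sign reverses if r exceeds 1. All non-zero figures are illustrations resting on an assumed r, equal logging and the planned segment lengths. The PR analysis has the same gap, of unknown size.

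This should be fixed. Confidence is medium, because the sponsor may already intend a motion-only analysis and no changed conclusion can be demonstrated.

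**What to change.** - State in Section 8 that the SpO2 and PR Arms supporting the motion claim use only points from the 2Hz, 4Hz and Rand segments.
- Report the no-motion Arms separately as a baseline.
- Reconcile the 90 s hold in Section 3 with the 120 s sequence in Section 5, so that the data belonging to each segment are defined.

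The cost is one or two sentences in Section 8, the timing reconciliation and a segment flag in the dataset. The documents do not say whether the SD-card record carries segment times, so the sponsor should confirm that segments can be identified. No extra data collection is needed.

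Planned data time per sensor for the motion Arms falls from 4,800 s to 3,600 s under reading (a) (1,200/4,800 = 25%) and from 3,600 s to 2,400 s under (c) (1,200/3,600 = 33%). It does not change under (b). Only still-hand time is removed. The reported figure may become slightly less favourable, depending on r.
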